## **12.5 Early Study Stopping Rule For Excessive Toxicity**

Any grade 4 or 5 study-related toxicity in pamidronate-treated participants will result in a pause in study randomization for a re-evaluation of the treatment plan.

In addition to the foregoing, three toxicities will be monitored in participants in both the pamidronate and control groups: uveitis, atrial fibrillation, and osteonecrosis of the jaw (ONJ) of grade 3 or higher (as these toxicities will be recorded only if they are of grade 3 or higher). These toxicities will be monitored at interim analyses by comparing the two groups using a Lan-DeMets stopping rule with an O'Brien-Fleming alpha-spending function. For this monitoring purpose,

the outcome for each participant will be the count of AEs of any of these three types, and the P-value for comparing the groups will be computed using a permutation test that permutes groups labels on participants, with test statistic the difference between groups in their average numbers of AEs. Interim analyses will be performed every 6 months.

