## 9.2 Documentation of Adverse Events

The goal of AE monitoring will be to focus on events that are related directly to study participation, not the transplant procedure or the disease under treatment unless study participation exacerbates the event. Due to the complex medical condition of the post-transplant patient, monitoring for adverse events will focus on events beginning with the 1st dose of pamidronate through the Day 360 visit.

For patients assigned to pamidronate, a toxicity assessment will be done in conjunction with each infusion (Day 90, 180, and 270) at the following time points:

- Prior to the pamidronate infusion - within 72 hours before the infusion
- 1 week (+/- 3 days) after each pamidronate infusion via telephone interview
- At any unplanned visit

At each of these time points the worst grade of the targeted toxicity since the previous assessment will be recorded in addition to any unexpected toxicities felt at least possibly related to pamidronate.

Of special concern are rare, but potentially serious risks associated with pamidronate which, if serious enough will lead to the discontinuation of the study drug per section 12.5. These targeted toxicities (based on CTCAE v4) will be collected on all patients (control and pamidronate) are:

- Anterior uveitis by subject's report (blurred vision, eye pain, redness, sensitivity to light, irregular pupil)
- Atrial fibrillation by the subject's report (palpitations, chest pain, shortness of breath)
- Osteonecrosis of the jaw by subject's report (jaw pain, swelling, redness, or other signs of infection in the gums, gums or sockets that don't heal after dental work, numbness or a heavy feeling in the jaw, draining of pus, visible bone in the mouth, roughness of the gums in a particular area) and/or physical examination at study visits.

All targeted toxicities, regardless of grade, and other events, grade 3 or greater that are felt at least possibly related to study treatment or cannot be explained by another cause (i.e. unexpected, not related to transplant, disease for which the transplant was done, underlying medical condition, etc.) will be recorded in OnCore for all patients.

After completion of the targeted toxicity form at day 360 formal collection of adverse events ends; however the sponsor/investigator must report upon knowledge any treatment related event meeting the expedited reporting criteria found in section 9.1 regardless of timing to pamidronate.

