## **12 Statistical Considerations**

### **12.1 Sample Size**

Sixty (60) subjects total (30 each in the Control and Pamidronate groups) gives 80% power to detect a difference between groups of 0.75 standard deviations (SDs)

describing variation in LBMC within study group after adjusting for height, age, sex, Tanner score, and race. Adjusting for age and sex, this SD is 5-8g (46, 47); adjusting further for race and height should reduce this SD by about half (48-50). This gives a within-group SD of about 2.5-4g and a detectable difference of 2-3g. To have 60 evaluable subjects, 192 need to be screened to allow for a 50% consent rate, 10% death rate by Day 90, 20% death rate between Day 90 and Day 360, and 10% drop out after randomization.

Anticipated Enrollment Over Duration of Study

	Screen	Study Entry Day -14 a	Day 7	Day 14	Day 21	Day 90	Day 180	Day 270	Day 360
Total	192	96	96	96	96	86	86	86	60
University of Minnesota (UMN)	96	48	48	48	48	43	43	43	30
Fred Hutchinson Cancer Research Center	96	48	48	48	48	43	43	43	30
a Day 0 is the day of hematopoietic cell transplantation (HCT).									

According to data from 2011 to 2012, 36 allogeneic transplants have been performed at UMN and 37 have been performed at Fred Hutchinson Cancer Research Center. It is expected that screening 28 patients per year will be feasible for both sites.

It anticipated that enrollment will take 3.5 years.

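### Section 12.5's between-arm toxicity boundary is close to inert during accrual: under the usual two-sided 0.05 it cannot cross at the 6- or 12-month look and needs six affected children against none at the end

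*Combined protocol and SAP*

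**What the plan says.** Section 12.5 has two parts. In the first, "Any grade 4 or 5 study-related toxicity in pamidronate-treated participants will result in a pause in study randomization". In the second, events in both arms are compared. The events are "uveitis, atrial fibrillation, and osteonecrosis of the jaw (ONJ) of grade 3 or higher", and the method is "comparing the two groups using a Lan-DeMets stopping rule", with O'Brien-Fleming-type alpha spending. The outcome is each participant's count of such events, and the p-value comes from a "permutation test that permutes groups labels on participants, with test statistic the difference between groups in their average numbers of AEs". On timing, "Interim analyses will be performed every 6 months".

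Section 9.2 introduces these toxicities with the words "Of special concern are rare, but potentially serious risks associated with pamidronate". It refers to section 12.5 for the consequences.

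Section 12.5 does not state the overall alpha, whether the test is one- or two-sided, the information scale, the number of looks, a boundary table, or how often the rule would trigger at any toxicity rate.

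**The concern.** O'Brien-Fleming-type spending releases almost no alpha at early looks. That is a usual choice for efficacy, where early stopping should be hard. For harm the priority is normally reversed. Here the spending function is joined to a two-group test on events that the protocol itself expects to be rare, with about 43 participants per arm. With so few events, a permutation p-value cannot become small unless a large share of the treated arm is affected.

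If so, a section titled as an early stopping rule contains a comparison that would seldom act while children are still being randomised. The DSMC could not see this from the protocol, because no boundary or operating characteristic is given.

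**Working it through.** **The plan's own figures.** Section 12.5 gives no figure to reproduce. Those in section 12.1 do reproduce. A two-sided 0.05 t-test with 30 per arm and a difference of 0.75 SD has power 0.815 (stated: 80%). The funnel is 192 × 0.5 = 96, × 0.9 = 86.4, × 0.7 = 60.5 (stated: 96, 86, 60).

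**Inputs.** 86 randomised, so 43 per arm at 1:1 (sections 12.1 and 12.3). Enrolment lasts 3.5 years and the study 4.5 years (section 13.6), which gives nine six-monthly looks. Randomization is at Day 90, so assignments lag the study start by about 3 months. Assumed: linear accrual of 86/42 = 2.05 per month, equal arms, information = month/54, two-sided 0.05 (0.025 in the harm direction).

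**Boundary.** Cumulative spending in the harm direction is a(t) = 2[1 − Φ(z/√t)], with z the upper 0.0125 normal point. Nominal p-values follow by recursive integration.

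**Smallest attainable p.** If k participants on pamidronate and none on control have one event each, the one-sided permutation p is C(n,k)/C(2n,k), with n per arm.

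| Month | n per arm | Nominal one-sided p | Fewest affected v 0 (its p) | Chance of having crossed at a 10% rate |
|---|---|---|---|---|
| 6 | 3 | 1.8e-11 | none (3 v 0 gives 0.05) | 0 |
| 12 | 9 | 2.0e-6 | none (9 v 0 gives 2.1e-5) | 0 |
| 18 | 15 | 1.03e-4 | 10 (1.00e-4) | under 0.001% |
| 24 | 22 | 7.4e-4 | 9 (7.0e-4) | 0.01% |
| 30 | 28 | 2.4e-3 | 8 (2.2e-3) | 0.5% |
| 36 | 34 | 5.2e-3 | 8 (2.5e-3) | 1.7% |
| 42 | 40 | 9.1e-3 | 7 (5.9e-3) | 10% |
| 48 | 43 | 0.0137 | 6 (0.0130) | 26% |
| 54 | 43 | 0.0190 | 6 (0.0130) | 26% |

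The last column is the binomial tail P(X ≥ k), X ~ Bin(n, 0.10), with no control events. The required k never rises, so having crossed earlier implies crossing now. It counts every event as seen at once, so it is an upper limit while follow-up is incomplete. At a 5% rate the final figure is 2%.

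**At the end.** 5 v 0 with 43 per arm gives two-sided p = 2 × 0.0276 = 0.055. It would fail even an unadjusted 0.05 test (0.052 with 30 per arm). With one affected control 8 are needed, and with two, 10.

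**Unit.** The labels are permuted on participants, so six events crowded into three children give two-sided p = 0.24 and do not cross.

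**Sensitivity to what is not stated.**
- One-sided 0.05: from month 12 the minimum is 9 (of 9), 9, 8, 7, 6, 6, 5, 5. At a 10% rate the chance is 21% by month 42 and 43% by the end.
- Randomised fraction as information: the end is still 6 v 0.
- Clock from first randomization: 12 per arm at 12 months. Crossing becomes possible, but only at 11–12 of 12 v 0 (9–10 of 12 at one-sided 0.05).
- Largest imbalance the blocks allow (2 × 2 strata × 2 sites = 8, so 39 v 47): 5 v 0 gives one-sided p = 0.017 and would cross at the end.

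**Pocock-type spending at the same alpha**, a(t) = α ln[1 + (e − 1)t]. At one-sided 0.025 it needs 6 v 0 at month 12 and 7 v 0 from month 18 to the end. At one-sided 0.05 it needs 6 v 0 from month 12 to the end. By month 42 the requirement equals the O'Brien-Fleming one (7 v 0 and 6 v 0), and at the end it is one participant worse.

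**The case against.** The strongest reply is that protection does not rest on this boundary. Any single related grade 4 or 5 toxicity on pamidronate pauses randomization. Section 9.5 makes each grade 3 or higher targeted event, in either arm, reportable as a stopping-rule event. Section 9.4 has the affiliate report such events within 24 hours, and section 10.4 has the DSMC review the study at least quarterly. All of this stands. A reader might infer from the table that early participants have no effective safety stop, and the documents do not support that. What is missing is narrower: a stated count that triggers action for grade 3 events and for events judged unrelated. Attribution is hard after transplant, as section 9.2 acknowledges in describing these patients' complex condition.

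Second, a flat statement that the rule cannot cross in the first year, or always needs 6 v 0, goes beyond the documents, because alpha, sidedness and the clock are unstated. One-sided 0.05 is a reasonable choice for harm. It lowers the final requirement to 5 v 0 and makes month 12 crossable, though only if all 9 treated children are affected.

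Third, a concurrent control separates drug effects from transplant effects, and a single-arm trigger does not. Section 12.5 monitors both arms on purpose, and the revision history says that it was revised in response to DSMC concerns. This is a good reason to keep the comparison, but not to make it the only numerical trigger for these events. It is also tempting to set a single-arm rule's stopping probability beside the 26%. That is not like for like, because the false-stop rates and the use of controls differ.

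**Conclusion.** The concern holds as a design weakness of limited scope. Under two-sided 0.05, with time from study start, the comparison cannot cross at the first two looks, needs 7 to 10 affected treated children against none from month 18 to month 42, and needs 6 v 0 at the end. At a true 10% rate with no control events it acts by month 36 less than 2% of the time, by month 42 at most about 10%, and ever about 26%. At one-sided 0.05 the figures for month 42 and the end are 21% and 43%, with 5 v 0 at the end.

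These results rest on an assumed alpha, sidedness, information scale and even accrual. The 10% rate is illustrative, since the documents give no expected rate. The alternatives tried leave the early looks practically closed. For grade 3 events, and events of any grade judged unrelated, no count likely to occur would trigger action during most of accrual.

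**What to change.** Amend section 12.5.

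1. Keep the between-arm comparison. State its overall alpha, sidedness, information scale and planned looks, and add the resulting boundary table in affected participants.
2. Add an exact sequential boundary on the number of pamidronate participants with a grade 3 or higher targeted event, against an acceptable rate set by the DSMC. Crossing leads to a pause in randomization and DSMC review, with the control data in hand.
3. State how often each rule triggers over a range of true rates, at the actual look schedule. As an illustration only, a boundary of 2, 3, 3 and 4 affected, applied at 10, 20, 30 and 43 treated participants, stops 71% of the time at a true 10% rate and 3.5% at 2%. The 2% is an assumption, and the DSMC's rate would change the boundary.
4. Reconcile the recording of these events: section 12.5 says only grade 3 or higher are recorded, whereas section 9.2 records them at any grade.

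Replacing O'Brien-Fleming with Pocock spending at the same alpha does not do the job, as shown above.

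The cost is one amended section, with no extra participants or data. The downsides are a small, stated chance of an unnecessary pause, and a trigger that cannot by itself tell drug from transplant effects. The control comparison is kept for that purpose.

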## **13 Ethical and Regulatory Considerations**

### **13.1 Good Clinical Practice**

The study will be conducted in accordance with the appropriate regulatory requirement(s). Essential clinical documents will be maintained to demonstrate the validity of the study and the integrity of the data collected. Master files should be established at the beginning of the study, maintained for the duration of the study and retained according to the appropriate regulations.

### **13.2 Ethical Considerations**

The study will be conducted in accordance with ethical principles founded in the Declaration of Helsinki. The IRB will review all appropriate study documentation in order to safeguard the rights, safety and well-being of the patients. The study will only be conducted at sites where IRB approval has been obtained. The protocol, informed consent, written information given to the patients, safety updates, annual progress reports, and any revisions to these documents will be provided to the IRB by the investigator.

### **13.3 Inclusion of Minorities**

There are no opportunities for any active recruitment or outreach efforts that may increase minority participation beyond that of the pool of transplant patients that is referred to us.

The ethnic representation of the population within the catchment area in the states of Washington and Minnesota according to 2010 census is as follows:

- American Indian/Alaska Native 1-2%
- Asian 6-7%
- Native Hawaiian or Other Pacific Islander 0.04%
- Black or African American 4-8%
- White 79-81%
- More than one race 3-6%

The ethnic representation of children who received transplant at both institutions over the last 2-6 years is as follows:

- American Indian/Alaska Native 1-3%

- Asian 7-11%
- Native Hawaiian or Other Pacific Islander 0-1.5%
- Black or African American 1.5-9%
- White 72-77%
- more than one race 3-4%

This study has no exclusions based on race or ethnicity and will be presented to every patient who is referred for HCT who meets the eligibility criteria. Our efforts will focus on making sure that potential study subjects who are in the minority groups are enrolled in the study. We do expect minority representation in the study as indicated in the enrollment table based on the ethnic distributions of patients referred to both transplant centers in Minnesota and Washington. We will employ the following specific efforts to make sure that every ethnic minority patient with a hematologic malignancy or severe aplastic anemia who is referred for HCT will be given an opportunity to participate in the study (as listed in the enrollment table, particularly 7 Asians and 6 African Americans):

- At each transplant center the standard practice is that every patient who is referred for transplant is reviewed by a transplant coordinator for all open research studies that they would potentially be eligible for. Since a transplant coordinator is aware of all incoming patients, a transplant coordinator will then notify the study coordinator and a study PI (either myself or one of the study's co-investigators) about the appointment time for a pre-HCT evaluation who will be on site at the time of the visit. The study will be reviewed with the patient/family by a nurse coordinator for general overview information and this is then followed up with a meeting led by an attending transplant physician and a study PI (either myself or one of the study's co-investigators) where specific details of each study are presented, risks/benefits explained, and informed consent obtained.
- Since each transplant program has access to culturally diverse healthcare interpreters, we will make sure that they are present at the time of the visit to assist in explaining the study and reviewing the consent forms for any non-English speaking minority patients as well as those who speak English, but are not native English speakers. To ensure a culturally sensitive approach in the recruitment of minority subjects who may have English as their first language, we will consult with or include in the consent meeting an impartial staff member (RN, advanced practice provider, social worker) of the same minority as the subject who would be able to facilitate verbal communication and interpretation of culturally sensitive issues even if language is not a barrier. We have confirmed that both institutions have staff members in the transplant programs

that represent at least individuals of African American, Hispanic and Asian descent.

- Patients and/or their parents/guardians will be given the option of taking copies of the consent documents with them with a phone number for the interpreter, and the study coordinator who will contact the patient or parents/legal guardians within a few days to schedule a screening visit if they are interested in participating.
- Fear and mistrust about clinical research is not uncommon, especially among minorities. Study staff and nurses in the clinic will take care to spend time educating each potential participant about clinical research and the goals of this study.

#### **13.4 Informed Consent**

All potential study participants will be given a copy of the IRB-approved consent to review. The investigator or designee will explain all aspects of the study in lay language and answer all questions regarding the study. If the participant (parents/guardians for minors with assent for minor 7 years and older) decides to participate in the study, he/she will be asked to sign and date the consent document. Patients who refuse to participate or who withdraw from the study will be treated without prejudice.

#### **13.5 Protocol Amendments After Study Initiation**

Should changes in the study plan or protocol become necessary in the course of the clinical trial, those specific changes will be discussed and agreed upon by the Sponsor, Investigator, and appropriate IRB approval obtained before the changes are implemented. All changes must be documented as protocol amendments. As a study conducted under an Investigational New Drug (IND), FDA notification may be required in addition to the IRB approval.

#### **13.6 Anticipated Duration of the Clinical Investigation**

Each subject will be enrolled in the study for approximately 1 year. It is expected that each of the study sites will screen 28 patients per year for 3.5 years with the final subject completing study participation 4.5 years after study initiation. The final study report will be completed approximately 5 years after study initiation.

If the study is terminated prior to completion, a closeout report will be filed with the Institutional Review Board (IRB) within 3 months of study termination.

## Appendix I – Eligibility Checklist

Refer to the Eligibility Checklist Case Report Form (CRF)

## Appendix II – Food Frequency Questionnaire

### Food Frequency Questionnaire

Name/Age:

Date:

We would like to know about some of the foods you eat. For each food listed please fill in how often you usually eat a portion of the size stated. If you eat the food:

- Every day or more than once a day, fill in how many times you have it per day
- Less than once a day but more than one a week, fill in the times per week
- Less than once a week, but more than once a month, fill in the times per month
- Less often than once a month, or never eat it, put an “X” under “do not eat”.

---

Example: Janice has a glass of orange juice every morning, along with two slices of toast. She usually has two sandwiches at lunch, and eats French fries about 3 times per week. She almost never eats cauliflower.

	Per Day	Per Week	Per Month	Don't Eat
Orange juice, 1 cup	1			
French fries, regular serving		3		
Cauliflower, 1/2 cup				X
Bread or toast, 1 slice	6			

---

### NUMBER OF TIMES I EAT THIS FOOD

	Per Day	Per Week	Per Month	Don't Eat
Bread or toast, 1 slice or 1 roll				
Muffin, 1 large				
Pizza, 1 medium slice				
Cheeseburger or veggie burger				
Cheese: 1 slice processed OR 1 piece hard cheese (plain or in sandwich)				
Broccoli, 1/2 cup				
Ice Cream, 1/2 cup				
Frozen yogurt, 1/2 cup				
Milkshake, 11 oz				
Cottage cheese, 1/2 cup				
Yogurt, 8 oz (small carton)				
Soft drink, 12oz				
Tofu, 2 oz				
Milk on cereal, 1 cup				
Orange juice, 1 cup				

Milk (any type), 1 cup				
Macaroni & cheese, 1 cup				

Is your orange juice fortified with calcium?

No  
 Yes

Formula Intake

Not Applicable

Formula Information: \_\_\_\_\_ ➤ Name/Brand: \_\_\_\_\_

Volume/Day \_\_\_\_\_ or \_\_\_\_\_  
(oz) (ml)

Are you allergic to any foods?

No

Yes: what foods? \_\_\_\_\_

**THANK YOU!**

**Completed By:** \_\_\_\_\_

**Date:** \_\_\_\_\_

### Appendix III - Physical Activity Questionnaires

#### Outdoor Playtime Recall Questionnaire

Think for a moment about a typical weekday for your child **in the past 7 days**.

1. How much time would you say your child spends playing outdoors on a typical weekday?

\_\_\_\_\_ Hours \_\_\_\_\_ Minutes

Now think about a typical weekend day for your child **in the last month**.

2. How much time would you say your child spends playing outdoors on a typical weekend day?

\_\_\_\_\_ Hours \_\_\_\_\_ Minutes

3. How many hours per day, **during the week**, would you say your child spends watching television in each season of the year?

\_\_\_\_\_ Too young, does not watch TV

\_\_\_\_\_ Spring \_\_\_\_\_ Summer \_\_\_\_\_ Fall \_\_\_\_\_ Winter

4. **On Saturday and Sunday**, how many hours per day, does your child spend watching television in each season of the year?

\_\_\_\_\_ Too young, does not watch TV

#### Saturday:

\_\_\_\_\_ Spring \_\_\_\_\_ Summer \_\_\_\_\_ Fall \_\_\_\_\_ Winter

#### Sunday:

\_\_\_\_\_ Spring \_\_\_\_\_ Summer \_\_\_\_\_ Fall \_\_\_\_\_ Winter

5. How many hours per day, **during the week**, does your child recreationally use the computer, play video games or participate in other screen-related activities in each season of the year?

\_\_\_\_\_ Too young, does not watch TV

\_\_\_\_\_ Spring \_\_\_\_\_ Summer \_\_\_\_\_ Fall \_\_\_\_\_ Winter

**6. On Saturday and Sunday**, how many hours per day does your child recreationally use the computer, play video games or participate in other screen-related activities in each season of the year?

\_\_\_\_\_ Too young, does not watch TV

